##### 4.3.1.2.1. Pharmacokinetic Concentrations Listings

The PK concentration data will be listed by analyte (EE, LNG and GSK3036656), treatment, day, time and subject for the PK analysis set. Concentration listings will include nominal PK sampling time, actual sampling times, time deviation, and actual relative time, and concentrations. Plasma concentrations below the lower limit of quantification (LLOQ), i.e. non-quantifiable (NQ), will be presented as NQ in the listings and the LLOQ value presented as a footnote.

##### 4.3.1.2.2. Pharmacokinetic Concentration Summary Tables

PK concentration data will be reported according to GSK data standards.

For summary tables, all NQs will be replaced with zero for the calculation of median and mean profile however for geometric mean and geometric CV% NQ values will be replaced by half the LLOQ value, refer [[GSK, VQD-REF-015788](#)] Non-Compartmental Analysis of Clinical Pharmacokinetic Data (Section 7 References) for more details.

Summary statistics will not be calculated if there are less than 3 participants with quantifiable concentrations at a scheduled timepoint. The statistics will be reported as NC, with the exception of minimum and maximum; minimum will be reported as “NQ” and in case of all NQ values, the maximum will also be reported as NQ.

Data in concentration summary tables will be reported as per IDSL reporting standards.

#### **4.3.1.2.3. *Pharmacokinetic Concentration Figures***

Comparative linear and semi-logarithmic plots of the median (range) and mean ( $\pm$ SD) concentration-time data for each analyte will be prepared. A reference line indicating LLOQ will be included on plots.

For median and mean profiles, PK concentrations that are NQ will be handled as follows:

- All NQ values will be set to zero except when an individual NQ falls between two quantifiable values, in which case it will be omitted from the calculation of mean or median profiles.
- Measurable concentrations which follow more than one consecutive mid-profile NQ will be set to missing.

Figures will report mean / median values below the LLOQ of the assay, if obtained. For linear plots, zero concentration value(s) will be included in the plot. For log-linear plots, zero concentration value(s) will be assigned a missing value.

Individual concentration-time time will be plotted vs actual sample times, in linear and log-linear scale. For individual linear and log-linear figures NQ values will be substituted as follows:

- NQs at the beginning of a participant profile (i.e., before the first incidence of a measurable concentration) will be assigned to zero. For linear plots, zero concentration values at the beginning of a participant profile will be included in the plot; when using log-linear scale, zero values will be considered missing.
- NQs at the end of a participant profile (i.e., after the last incidence of a measurable concentration) will be set to missing.
- Single NQs which fall between two measurable concentrations will be set to missing.
- Consecutive NQs which fall between measurable concentrations will be set to zero and for individual subject plots
- Measurable concentrations after consecutive NQs will be retained.

#### **4.3.1.2.4. *Pharmacokinetic Parameter Listings***

The PK parameters will be listed by participant for the PK analysis set. The PK parameters that will be flagged and/or excluded from summary tables and statistical analyses will be flagged and footnoted in the listing with the reason for flagging/exclusion. In case of  $C_t$  concentrations that are NQ, they will be presented as NQ in parameter listings.

#### **4.3.1.2.5. Pharmacokinetic Parameter Summary Tables:**

Biostatistics group will consider the derived PK parameters as source data and will use this data without rounding for calculation of PK parameters summary statistics tables.

The PK parameters will be summarized by analyte, treatment, and day for the PK analysis set; for more details, refer to Section 4.1.1 General Methodology.

PK parameters that are not determined (ND) because the planned calculation could not be adequately performed will be assumed missing in both descriptive and statistical analyses and no imputation will be performed.

In case of  $C_t$  concentrations that are NQ, for PK parameter summary tables they will be handled with the same rules described as for concentration summary tables.

Data in PK parameter summary tables will be reported as per IDSL reporting standards.

#### **4.3.2. Secondary Safety endpoint(s)**

A secondary objective of this study is to assess that GSK3036656 and Microgynon taken alone or together are safe and well tolerated in healthy female participants of non-childbearing potential. Safety endpoints assess the incidence of safety events occurring during each treatment period.

##### **4.3.2.1. Definition of [endpoint(s)/estimands]**

The secondary safety endpoints and attributes of the estimands are detailed in Section 1.1

##### **4.3.2.2. Main analytical approach**

All safety analyses will be performed on the Safety Population. Safety data will be presented in tabular format by treatment groups (Microgynon, GSK3036656 and Microgynon+GSK3036656) and summarized descriptively according to GSK's Integrated Data Standards Library. For each treatment group, the denominator for percentages (N) will be the number of participants entering the associated treatment period. No formal statistical analysis of the safety data will be conducted. Unless otherwise specified, available data will be analyzed as collected regardless of intercurrent events that may occur (treatment policy). Missing data will not be imputed.

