**Table 3 Objectives and Endpoints**

Objective(s)	Endpoint(s)
Primary	
To assess the effect of steady state exposure of GSK3036656 on the single dose PK of EE and LNG in healthy female participants of non-childbearing potential	Area under the plasma concentration-time curve to infinity AUC(0-inf) and maximum observed concentration (C max ), after a single dose of EE and LNG (EE AUC (0-inf) , EE C max , LNG AUC (0-inf) , LNG C max )
Secondary	
To characterize the steady state PK of GSK3036656 in the presence of EE/LNG	AUC(0- $\tau$ ), C max , C t (Day 8, 10, 12, 15 and 16) and time of maximum observed concentration (T max ) for GSK3036656
To characterize the single dose PK of EE/LNG alone and in the presence of GSK3036656	AUC(0-t), T max and t 1/2 for EE and LNG, in Treatment Period 1 and Treatment Period 3.
To assess the safety and tolerability of GSK3036656 and Microgynon when given alone or in combination in healthy female participants of non-childbearing potential	
 
• Incidence of SAEs within each treatment period.
 
• Incidence of AEs of grade 3 severity or higher within each treatment period.
 
• Incidence of AEs considered by the investigator to be possibly, probably, or definitely related to study drug within each treatment period (overall and separately for relationship to Microgynon and to GSK3036656).
 
• Incidence of participants withdrawn from the treatment/study due to adverse events within each treatment period.
 

Objective(s)	Endpoint(s)
	
 
Incidence of ECG values PCI within each treatment period.
 
Incidence of clinical chemistry laboratory values of PCI within each treatment period.
 
Incidence of hematology laboratory values of PCI within each treatment period.
 
Incidence of vital signs parameters of systolic blood pressure (SBP), diastolic blood pressure (DBP) and heart rate (HR) of PCI within each treatment period.
 

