##### 9.3.4.1.1. Adverse Events (AEs)

Adverse events will be coded using the MedDRA (Medical Dictionaries for Regulatory Activities) coding system.

Counting of AEs will be based on the number of participants, not the number of AEs. In addition to all adverse events, there will be separate summaries for:

- SAEs
- Severe AEs (AEs with a grade of 3 or higher)
- Drug-related AEs
  - Microgynon
  - GSK3036656
- AEs leading to study withdrawal
- AEs leading to study treatment discontinuation

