### 6.2.4. Study Period

Assessments and events will be classified according to the time of occurrence relative to the study intervention period.

Treatment period 1 ranges from Day 1 dose to Day 4 predose, similarly treatment period 2 ranges from Day 4 dose to Day 15 predose and treatment period 3 ranges from Day 15 dose until Day 18.

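### AE incidence is tabulated in treatment columns observed for about 3, 11 and 3 days with no stated exposure measure, so GSK3036656 alone cannot be read fairly against either other column.

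*SAP*

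**What the plan says.** The safety objective in Protocol Table 3 is "To assess the safety and tolerability of GSK3036656 and Microgynon when given alone or in combination". The endpoints are incidences within each treatment period.

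On layout, SAP 4.3.2.2 says: "Safety data will be presented in tabular format by treatment groups (Microgynon, GSK3036656 and Microgynon+GSK3036656) and summarized descriptively". Protocol 9.3.4.1 says the same. On the denominator, SAP 4.3.2.2 says "the denominator for percentages (N) will be the number of participants entering the associated treatment period". On the counting unit, Protocol 9.3.4.1.1 says: "Counting of AEs will be based on the number of participants, not the number of AEs".

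SAP 6.2.4 sets the windows: "Treatment period 1 ranges from Day 1 dose to Day 4 predose", then "treatment period 2 ranges from Day 4 dose to Day 15 predose and treatment period 3 ranges from Day 15 dose until Day 18".

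Two other rules bear on the middle column. SAP 6.2.8 places AEs with a partial start date in Period 2 unless the available data rule that out, and it bars imputed dates from deriving study day, time to onset or duration. Under SAP 6.2.4, an event that starts after the Day 4 dose belongs to Period 2, even if the investigator attributes it to the Day 1 Microgynon dose.

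Both documents rule out formal statistical analysis of safety data.

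**The concern.** A cell in these tables estimates the chance of at least one AE during the window, and that chance grows with the window. The columns carry treatment names rather than period lengths, and the objective speaks of the drugs alone and in combination, so readers will compare across columns. With no formal analysis planned, the table is all they have to judge from.

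Two misreadings are possible. GSK3036656 alone could seem less well tolerated than Microgynon or the combination only because it was watched for longer. Conversely, a higher daily risk on the combination than on GSK3036656 alone could go unseen because its window is roughly a quarter as long (3/11 = 0.27). Neither document states a quantity that would let a reader separate the two explanations.

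**Working it through.** **Inputs from the documents.** Period lengths follow from SAP 6.2.4: 4 − 1 = 3 days, 15 − 4 = 11 days, 18 − 15 = 3 days. The end of Period 3 is given only as Day 18. Discharge follows the 72-hour sample (Protocol Table 1), which supports 3 days, but a date-based count could treat Day 18 as a fourth day. Enrolment is about 20, which reproduces from SAP Section 5 as 16/(1 − 0.20) = 20. The plan gives no AE incidence or rate to reproduce.

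**Assumed input.** The documents give no daily AE risk. I take it as constant and the same in all periods, ranging from 0.5% to 10% per day.

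**Crude incidence.** The expected share with at least one AE over d days at daily risk h is 1 − (1 − h)^d.

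| h per day | 3 days | 11 days | ratio 11:3 | 4 days | ratio 11:4 |
|---|---|---|---|---|---|
| 0.5% | 1.5% | 5.4% | 3.59 | 2.0% | 2.70 |
| 1% | 3.0% | 10.5% | 3.52 | 3.9% | 2.66 |
| 2% | 5.9% | 19.9% | 3.39 | 7.8% | 2.57 |
| 5% | 14.3% | 43.1% | 3.02 | 18.5% | 2.32 |
| 10% | 27.1% | 68.6% | 2.53 | 34.4% | 2.00 |

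For rare events the ratio approaches 11/3 = 3.67. For common events it shrinks, to 1.87 at 20% per day.

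**Masking.** Let daily risk be 1% on GSK3036656 alone and 3% on the combination. The crude table expects 1 − 0.99^11 = 10.5% alone and 1 − 0.97^3 = 8.7% combined. If Day 18 counts in full, the combination shows 1 − 0.97^4 = 11.5%. A threefold rise would look like no difference under either count.

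**With an exposure measure.** If 20 participants complete, the columns hold 20 × 3 = 60, 20 × 11 = 220 and 20 × 3 = 60 participant-days. At equal daily risk the expected onset rates agree across columns. In the masking example the expected onsets are 220 × 0.01 = 2.2 and 60 × 0.03 = 1.8, that is 1.0 and 3.0 per 100 participant-days. The tripling is visible in expectation, though it rests on about two events per column.

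**What is not affected.** Microgynon alone and the combination both have windows of about 3 days. Counting Day 18 in full moves that comparison only from 3.0% against 3.0% to 3.0% against 3.9% at 1% per day. Laboratory, ECG and vital-sign summaries of potential clinical importance are not affected in the same way. SAP Table 2 schedules assessments on Days 1, 4, 15 and 18, which gives each period one planned post-baseline assessment whatever its length.

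**The case against.** The strongest reply is that the table delivers exactly what was declared. The endpoint is incidence within each period, and the estimand's summary is a percentage of those entering it. The objective is to assess safety, and no contrast between columns is an endpoint. Period days are disclosed in both documents. This stands, and it limits the point to an addition rather than a correction.

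Second, the comparison closest to the study's purpose, Microgynon with and without GSK3036656, uses windows of about equal length, both inpatient. This also stands. A reader might infer that an excess on the combination is hidden altogether. The documents do not support that, because masking arises only against GSK3036656 alone.

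Third, constant and equal daily risk is doubtful here. Period 2 opens with a loading dose and is mostly dosed at home, the other periods are inpatient, and the sequence is fixed. Dividing by days removes none of this. If AEs cluster early in dosing, an 11-day average could flatter GSK3036656 alone. These limits are real and belong beside the rates. They do not make the crude percentages comparable.

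Fourth, the full list of displays sits in the Output & Programming Specification (SAP 4.1.1), and the summaries follow the sponsor's data standards library. Neither is available to us. A reader might infer that no exposure measure will be produced, but the documents show only that none is stated in the protocol or SAP.

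**Conclusion.** The point holds for AE incidence whenever GSK3036656 alone is compared with either other column. The unequal windows follow directly from SAP 6.2.4. The size does not come from the documents. It is about 2.5 to 3.6 times under a constant, equal daily risk of 10% down to 0.5%, and 2.0 to 2.7 times against the combination if Day 18 counts as a full day. It should be quoted as a range with that assumption, not as a fixed factor of three.

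The default placement of partial-dated AEs and the assignment of late Microgynon events both push counts towards the same column. Their size cannot be judged in advance.

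A reader might infer that the safety objective formally contrasts each drug with the combination, or that the safety conclusions are invalid. Neither follows: the analysis is secondary and descriptive, and no decision rule is attached. The primary analysis and the sample size are untouched. This is a low-cost improvement to how the tables can be read.

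**What to change.** Keep the crude percentages. In the any-AE and drug-related AE tables, add for each column:

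- total participant-days of observation in the period;
- AE onsets per 100 participant-days, with total period days as denominator. This needs no time to onset, so it does not conflict with the SAP 6.2.8 rule on imputed dates. Label the row as counting events, because the percentages count participants;
- a footnote giving the period lengths (including how Day 18 is counted), the inpatient and outpatient difference, and the number of partial-dated AEs assigned to Period 2 by default.

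Two tempting alternatives are worse. A column limited to Days 4 to 6, to match the other windows in length, would collect the AEs imputed to the Period 2 start date and would cover the loading dose and the days just after Microgynon. A rate based on time to first event would need onset times that SAP 6.2.8 does not allow for imputed dates. Rates for grade 3 or higher events are not worth adding at this exposure.

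The cost is two rows and a footnote in two sets of tables, with no new data. The downside is that rates from about 60, 220 and 60 participant-days are imprecise and leave differences in setting, dose and sequence in place, so they should stay descriptive.

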###### **4.3.2.2.1. Adverse Events (AEs)**

An adverse event (AE) is considered study intervention emergent if the AE onset date is on or after study intervention start date for each treatment period. All AE summaries will be based on study intervention emergent events unless otherwise specified. Serious Adverse Event (SAE) summaries will be based on all SAEs reported regardless of whether they meet the definition of study intervention emergent or not. All AE and SAE summaries will be by System Organ Class and Preferred Term (PT) only unless otherwise specified.

Adverse events will be coded using the latest version of the standard Medical Dictionary for Regulatory Activities (MedDRA dictionary) and graded by the investigator according

to the National Cancer Institute Common Terminology Criteria for Adverse Events [NCI-CTCAE version 4.03].

In addition to the summary of all AEs, including counts and percentages of participants with any AE, there will be separate summaries for:

- SAEs
- Severe AEs (AEs with a grade of 3 or higher)
- Drug-related AEs
  - Microgynon
  - GSK3036656
- AEs leading to study withdrawal
- AEs leading to study treatment discontinuation
- Most Common ( $\geq 5\%$ ) Adverse Events by Overall frequency

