### 1.2. Study Schema

**Figure 1** Study design overview

Participants progress immediately from the end of Treatment Period 1 to Treatment Period 2, with no washout required in between.

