### 10.3.3. Definition of TEAE

TEAE Definition:

 
• A TEAE is an event that emerges during treatment, having been absent pre-treatment or worsens relative to the pre-treatment state.
 

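### The SAP decides by onset date alone whether an AE is emergent in a period, while the protocol's definition also covers worsening; an AE kept on one record that worsens under GSK3036656 or the combination is missed in that column.

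*SAP*

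**What the plan says.** SAP 4.3.2.2.1 sets the rule: an AE "is considered study intervention emergent if the AE onset date is on or after study intervention start date for each treatment period". It gives the rule wide scope: "All AE summaries will be based on study intervention emergent events unless otherwise specified". The tables governed by it are all AEs, AEs of grade 3 or higher, drug-related AEs (separately for each product), AEs leading to study withdrawal, and AEs leading to treatment discontinuation. SAEs are handled differently: "Serious Adverse Event (SAE) summaries will be based on all SAEs reported regardless of whether they meet the definition of study intervention emergent or not".

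The definition in Protocol 10.3.3 is wider: "A TEAE is an event that emerges during treatment, having been absent pre-treatment or worsens relative to the pre-treatment state".

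The secondary safety endpoints in Protocol Table 3 are per-period incidences, for example "Incidence of AEs of grade 3 severity or higher within each treatment period". SAP 4.3.2.2 presents them by treatment (Microgynon, GSK3036656, both), with the number entering the matching period as denominator. SAP 4.7 reports no change from the analysis planned in the original protocol. The amendment's list of main changes does not mention Section 10.3.3.

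**The concern.** Every participant goes through the treatments in the same order, and the protocol adds: "Participants progress immediately from the end of Treatment Period 1 to Treatment Period 2, with no washout required in between". An AE that begins after Microgynon can therefore run on into GSK3036656 dosing, and one that begins on GSK3036656 can run on into the combination. If it worsens there, the worsening is information about the later treatment. A rule that looks only at onset does not register it in the later column.

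These columns are where a reader looks for the tolerability of GSK3036656 alone and with the contraceptive. With about 20 participants, one missed grade 3 event is the difference between an empty cell and 5%.

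**Working it through.** There is no stated figure to reproduce, so the check compares the texts and then applies the rules to assumed events.

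**The definitions.** SAP 4.3.2.2.1 tests one thing, the onset date against the start of treatment in the period. Protocol 10.3.3 has two limbs, absence before treatment or worsening: "having been absent pre-treatment or worsens relative to the pre-treatment state". The second limb has no counterpart in the SAP.

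**Does another SAP section supply it?** SAP 6.2.4 says: "Assessments and events will be classified according to the time of occurrence relative to the study intervention period". It bounds the periods (Day 1 dose to Day 4 predose, Day 4 dose to Day 15 predose, Day 15 dose to Day 18) but has no rule for a later rise in grade. The partial-date rules in SAP 6.2.8 place an AE through its start date and are also silent on worsening.

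**What is 'pre-treatment' here?** Protocol 10.3.3 does not say. Two features favour reading it period by period: the endpoints are incidences per period, and baselines are taken per period (SAP 4.1.2; the footnote to Protocol Table 1 makes Day 4 predose the baseline for GSK3036656).

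**Is a worsening AE a new record?** Neither document requires it. Protocol 10.3.4.5 has unresolved AEs reviewed at later visits and updates added to the existing documents. That points to one record but does not settle it.

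**Assumed events, each kept on one record with its original onset date:**
- Onset Day 2, worsens Day 9. Onset only: Period 1. Onset or worsening: Periods 1 and 2.
- Onset Day 6, worsens Day 16. Onset only: Period 2. Onset or worsening: Periods 2 and 3.
- Condition present before Day 1, worsens Day 9. Onset only: no period. Onset or worsening: Period 2. Protocol 10.3.1 makes such an exacerbation an AE, so it is lost only if the old onset date is kept.

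**Size.** One participant changes a column by 100/N percentage points, where N is the number entering the period:
- N = 20 (planned enrolment): 100/20 = 5.
- N = 16 (planned evaluable number, used here as a lower case): 100/16 = 6.25.

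**The case against.** The strongest reply has four parts.

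- **A headache that starts on Day 2 was absent before any treatment, so both documents already call it emergent.** That is fair if 'pre-treatment' means before the first study dose. Protocol 10.3.3 does not rule this out, and the protocol's endpoint and AE analysis sections do not use the term TEAE. So this is not a flat contradiction. What stands is that the SAP applies emergence to each period but drops the worsening limb without saying so.
- **Recording practice may cure it.** Protocol 10.3.1 describes an AE as something new or exacerbated, so a worsening could be entered as its own AE, and the onset rule would then place it correctly. The eCRF completion guidelines and the Output and Programming Specification, which were not available, may settle this. The point is therefore conditional.
- **A reader might infer that the participant moves from the later column to the earlier one, with the worst grade credited to Microgynon.** The documents do not support that. In the all-AE table the earlier column is right, because the event did begin there; the later column simply lacks a count. No section says that a single record carries its highest grade back to the onset period.
- **Other displays limit the harm.** SAE summaries are not filtered by emergence, although nothing reassigns a worsened SAE to the later period. Laboratory, ECG and vital-sign changes are measured against period baselines. An event judged related to GSK3036656 still appears in the table for that product. It would, however, sit in the column of the period in which it began, which may be the Microgynon-only one.

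**Conclusion.** The point holds in a conditional form. The SAP's rule is narrower than the protocol's definition, and the difference is not declared. If a worsening AE stays on one record with its first onset date, it is not counted in the period where it worsened. The GSK3036656 and combination columns can then be understated by 5 percentage points per affected participant at N = 20, or 6.25 at N = 16.

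This rests on two assumptions: that 'pre-treatment' is read period by period, and that sites do not open a new record when the grade rises. The documents give no basis for saying how often this will happen, so they do not support a conclusion that the SAP will in fact understate toxicity. Whether the earlier column also wrongly receives the higher grade depends on a grading convention that is not stated.

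The tables concerned are descriptive secondary safety displays, and the primary PK analysis is untouched. The change is still worth making, because it is small and improves attribution by treatment.

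**What to change.** In SAP 4.3.2.2.1, define an AE as emergent in a period if its onset, or an increase over the grade it had before that period's first dose, occurs after that dose. Count it in that period at the grade reached there. State that 'pre-treatment' is read period by period. In the eCRF completion guidelines, ask sites to record each grade increase with its own start date, so that the rule can be programmed. If the sponsor prefers onset only, SAP 4.7 should declare and justify the departure from Protocol 10.3.3.

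The cost is a few lines of SAP text, one recording instruction and a little more work at sites. A few events will appear in two columns, which a table footnote can explain.
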